**Table 1 Probability rates of individual participants for proposed loading and maintenance doses**

Loading Dose (mg) a	Probability Day 1 c	Maintenance Dose (mg) b	probability Day 14 d	Target Attainment Rate e
15	<1%	5	<1%	<1%
25	<1%	10	<1%	100%
50	<1%	20	<1%	100%
75	6.90%	30	5.80%	100%
a Day 1				
b Day 2-14				
c per trial probability of an individual participant exceeding the exposure limits [AUC 0-24 = 15 ug.h/mL or C max = 1.5 ug/mL] on Day 1 (simulations based on a lower limit of 75 mL/min for creatinine clearance)				
d per trial probability of an individual participant exceeding the exposure limits [AUC 0-24 = 15 ug.h/mL or C max = 1.5 ug/mL] on Day 14 (simulations based on a lower limit of 75 mL/min for creatinine clearance)				
e per trial probability of >90% of participants exceeding the target exposure for efficacy				

The starting dose regimen for this study will be 15 mg loading dose on Day 1 and 5 mg maintenance dose on Day 2-14, based on the above information, with the option to

investigate a lower dose in subsequent cohorts should the preliminary data indicate this is appropriate.

The loading dose (if applicable) and maintenance dose for each cohort will be chosen on the basis that it is not predicted to exceed the pre-specified safety cap, and the dose used will be decided by the Dose Escalation Committee (Section 11).

## 6. STUDY POPULATION

Prospective approval of protocol deviations to recruitment and enrolment criteria, also known as protocol waivers or exemptions, is not permitted.

### 6.1. Inclusion Criteria

Participants are eligible to be included in the study only if all the following criteria apply:

#### Age

1. Participant must be 18 to 65 years of age inclusive, at the time of signing the informed consent.

2.

#### Type of Participant and Disease Characteristics

3. New episode of untreated, rifampicin-susceptible pulmonary TB.
4. A chest X-ray picture which in the opinion of the Investigator is consistent with TB.
5. At least one sputum sample positive on direct microscopy for acid-fast bacilli (at least 1+ on the IUATLD/WHO scale) or molecular test (Xpert MTB/Rif) with result of either medium or high positive for MTB
6. Ability to produce an adequate volume of sputum as estimated from an overnight sputum collection sample (estimated 10 mL or more). (If less than 10 mL is collected overnight this may be repeated once).
7. Normal echocardiogram or echocardiogram with normal left ventricular function with at most trace to mild valvular regurgitation is allowed and no valvular stenosis.
8. Within the normal range for the assay for troponin at screening.
9. A creatinine clearance  $\geq 75$  mL/min (Cockcroft-Gault formula).

#### Weight

10. Body weight (in light clothing and with no shoes) between 40 and 90 kg, inclusive, at screening.

#### Sex

11. Male

##### a. Male participants:

A male participant with female partners of child-bearing potential must agree to use contraception as detailed in Section 13.6 (Appendix 6).

### Informed Consent

12. Capable of giving signed informed consent as described in Appendix 3 which includes compliance with the requirements and restrictions listed in the informed consent form (ICF) and in this protocol.

## 6.2. Exclusion Criteria

Participants are excluded from the study if any of the following criteria apply:

1. Evidence of a clinically significant (as judged by the Investigator) condition or abnormality (other than the indication being studied) that might compromise safety or the interpretation of trial efficacy or safety endpoints.
2. Poor general condition where any delay in treatment cannot be tolerated per discretion of the Investigator.
3. Clinically significant evidence of extrathoracic TB (miliary TB, abdominal TB, urogenital TB, osteoarthritic TB, TB meningitis), as judged by the Investigator.
4. QTcF > 450 msec.
5. History of allergy to any of the trial IP/s or related substances as confirmed by the clinical judgement of the Investigator.
6. Participants with vitiligo.
7. Current alcohol or drug abuse, that is, in the opinion of the Investigator, sufficient to compromise the safety or cooperation of the participant.
8. HIV infected participants:
  - a. having a CD4+ count <350 cells/ $\mu$ L;
  - b. or having received antiretroviral therapy medication within the last 30 days;
  - c. or having received oral or intravenous antifungal medication within the last 30 days;
  - d. or with an AIDS-defining opportunistic infection or malignancies [CDC, 1993] in the last 12 months (except pulmonary TB).
9. Participated in other clinical studies with investigational agents within 8 weeks prior to the first dosing day in the current study.
10. Participants with diabetes (Type 1 or 2), point of care HbA1c above 6.5 %, or random glucose over 11.1 mmol/L will be excluded from cohorts undergoing CCI

11. Treatment received with any drug active against Mtb (including but not limited to isoniazid, ethambutol, fluoroquinolones, rifampicin), or with immunosuppressive medications such as TNF-alpha inhibitors or systemic or inhaled corticosteroids (used for > 5 consecutive days), within 2 weeks prior to screening. Refer to the SRM for details.
12. Unavoidable treatment with prohibited concomitant medications (see SRM)
13. Participants with the following abnormal laboratory values at screening as graded by the enhanced Common Terminology Criteria for Adverse Events (CTCAE v 5 2017):
  - a. haemoglobin <10.0 g/dL; this criterion may be adjusted following DEC review (see Section 11).
  - b. thrombocytopenia grade 2 or greater (under  $50 \times 10^9$  cells/L);
  - c. serum potassium grade 2 or greater (<3.0 mEq/L);
  - d. aspartate aminotransferase (AST) grade 3 ( $\geq 3.0 \times$  ULN);
  - e. alanine aminotransferase (ALT) grade 3 ( $\geq 3.0 \times$  ULN);
  - f. APTT grade 3 ( $\geq 2.5 \times$  ULN)
  - g. INR grade 3 ( $\geq 2.5 \times$  ULN)
  - h. Total white cell count grade 3 (< $2.0 \times 10^9$  cells/L)

14.

CCI

### 6.3. Lifestyle Restrictions

#### 6.3.1. Meals and Dietary Restrictions

- Refrain from consumption of red wine, Seville oranges, grapefruit or grapefruit juice, from the day of start of study treatment until after the final dose.
- Water is allowed ad libitum.

#### 6.3.2. Caffeine, Alcohol, and Tobacco

- During each dosing session, participants will abstain from ingesting caffeine- or xanthine-containing products (e.g., coffee, tea, cola drinks, and chocolate) for 24 hours before the start of dosing until after collection of the final pharmacokinetic (PK) and/or pharmacodynamic sample.

- During each dosing session, participants will abstain from alcohol for 24 hours before the start of dosing until after collection of the final PK and/or pharmacodynamic sample.
- Use of tobacco products will be strongly discouraged from screening until after the final follow-up visit.

### **6.3.3. Activity**

- Participants will abstain from strenuous exercise for 48 hours before each blood collection for clinical laboratory tests. Participants may participate in light recreational activities during the study (e.g., watching television, reading).

## **6.4. Screen Failures**

Screen failures are defined as participants who consent to participate in the clinical study but are not subsequently randomised. A minimal set of screen failure information is required to ensure transparent reporting of screen failure participants to meet the Consolidated Standards of Reporting Trials (CONSORT) publishing requirements and to respond to queries from regulatory authorities. Minimal information includes demography, screen failure details, eligibility criteria, and any serious adverse events (SAEs).

## **7. TREATMENTS**

Study treatment is defined as any investigational treatment(s), marketed product(s), placebo, or medical device(s) intended to be administered to a study participant according to the study protocol.

## 7.1. Treatments Administered

Study Treatment Name:	GSK3036656	Rifafour e-275 (or equivalent generic alternative)
Dosage formulation:	Capsule	Tablet
Unit dose strength(s)/Dosage level(s):	1 mg or 5 mg or 25 mg GSK3036656 capsules (as free base equivalent)	Standard dose: 150/75/400/275 mg of Rifampicin, Isoniazid, Pyrazinamide and Ethambutol respectively per tablet
Route of Administration	Oral	Oral
Dosing instructions:	Refer to study reference manual	Refer to South African National TB Treatment Guidelines (including pyridoxine as required)
Packaging and Labelling	Study Treatment will be provided in HDPE bottles. Each HDPE bottle will be labelled as required per country requirement.	Will be provided by the manufacturer.
Manufacturer	WuXi AppTec (1 and 5 mg capsules) Aptuit (25 mg capsule)	Rifafour e-275: Sanofi-Aventis or appropriate alternative Equivalent Generic alternative to Rifafour e-275: Appropriate suppliers

**Rifafour e-275 (or equivalent generic alternative).**

Some participants will be treated with standard, intensive phase pulmonary TB treatment as recommended in the SA National TB Treatment Guidelines to verify that the laboratory assays used measure the expected magnitude of activity. This is HRZE (Rifafour e-275 or equivalent generic alternative) (HRZE: H=isoniazid: R=rifampicin: Z=pyrazinamide: E=ethambutol). The Rifafour e-275 (or equivalent generic alternative) treatment group is included as a benchmark for the EBA quantitative mycobacteriology and to evaluate whether HRZE in this population gives similar EBA results to that demonstrated in prior studies using this combination.

Rifafour e-275 (or equivalent generic alternative) Package Insert contains its known and potential risks and benefits.

**7.2. Method of Treatment Assignment**

On or prior to day 1, eligible participants will be assigned a unique number (randomization number) in ascending numerical order at the study site. The randomization number encodes the participant's assignment to one of the two arms of the study (GSK3036656 or standard-of-care), according to the randomization schedule generated prior to the study by the Statistics Department at GSK, using validated internal software. Once a participant number has been assigned to a subject, it cannot be re-assigned to another subject.

**7.3. Preparation/Handling/Storage/Accountability**

1. The Investigator or designee must confirm appropriate temperature conditions have been maintained during transit for all study treatment received and any discrepancies are reported and resolved before use of the study treatment.
2. Only participants enrolled in the study may receive study treatment and only authorized site staff may supply or administer study treatment. All study treatments must be stored in a secure, environmentally controlled, and monitored (manual or automated) area in accordance with the labeled storage conditions with access limited to the Investigator and authorized site staff.
3. The Investigator, institution, or the head of the medical institution (where applicable) is responsible for study treatment accountability, reconciliation, and record maintenance (i.e., receipt, reconciliation, and final disposition records).
4. Further guidance and information for the final disposition of unused study treatment are provided in the Study Reference Manual.
  - Under normal conditions of handling and administration, study treatment is not expected to pose significant safety risks to site staff.

Precaution will be taken to avoid direct contact with the study treatment. A Material Safety Data Sheet (MSDS) describing occupational hazards and recommended handling precautions will be provided to the Investigator. In the case of unintentional occupational exposure notify the monitor, Medical Monitor and/or GSK study contact.

## 7.4. Treatment Compliance

- Individual doses for a participant will be prepared from a bulk supply, the preparation of the dose will be confirmed by a second member of the study site staff.
- Participants are dosed at the site. They will receive study treatment directly from the Investigator or designee, under medical supervision. The date and time of each dose administered in the clinic will be recorded in the source documents. The dose of study treatment and study participant identification will be confirmed at the time of dosing by a member of the study site staff other than the person administering the study treatment. Study site personnel will examine each participant's mouth to ensure that the study treatment was ingested.

## 7.5. Concomitant Therapy

Any medication or vaccine (including over-the-counter or prescription medicines, vitamins, and/or herbal supplements) that the participant is receiving at the time of enrolment or receives during the study must be recorded along with:

- reason for use
- dates of administration including start and end dates
- dosage information including dose and frequency

The Medical Monitor should be contacted if there are any questions regarding concomitant or prior therapy.

Participants must abstain from taking prescription or non-prescription drugs (including vitamins and dietary or herbal supplements) within 7 days (or 14 days if the drug is a potential enzyme inducer) or 5 half-lives (whichever is longer) before the start of study treatment until completion of the follow-up visit, unless, in the opinion of the Investigator and Sponsor, the medication will not interfere with the study. A list of prohibited and permitted concomitant medication is provided in the SRM.

## 8. DISCONTINUATION CRITERIA

If study treatment/investigational product is interrupted or stopped this does not automatically result in the participant being withdrawn from the study. The investigator will make all effort to retain the patient in the study, provided the participant continues to provide their consent, and to complete and record all scheduled safety assessments required by the protocol. For the avoidance of all doubt: this does not prejudice the rights of the investigator and study participants under ICH GCP and under applicable laws. The study participant retains the right to withdraw consent at any time for any reason. The investigator also retains the right to withdraw the patients from the study if in the investigator's judgement, withdrawal is judged clinically necessary to protect a participant's safety.

If this results in the patient being placed on standard of care (i.e. Rifafour e-275 or equivalent generic alternative), then all assessments relevant to Rifafour e-275 (or equivalent generic alternative) will be performed as directed by the protocol (for

example, GSK3036656 pharmacokinetic assessments are not required, since the participant is not being dosed with GSK3036656).

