- B. Participants can proceed with the Visit 2 (day -2) assessments as soon as their Visit 1 (day -9 to -3) assessments have been completed i.e. Visits 1 and 2 may occur on the same day as long as the screening results are available in time for randomisation. Participants may be hospitalised during the entire pre-treatment period if the Investigator considers it advisable for reasons of safety or compliance.
- C. All events listed as occurring on Visit 5 (day 2) to Visit 10 (day 7) and Visit 12 (day 9) to Visit 16 (day 13) will be conducted each day during these visits.
- D. Height (m) will only be collected once at Visit 1 (day -9 to -3). A full physical examination will be performed at Visit 1 (day -9 to -3), with symptom-directed physical examinations at Visit 17 (day 14), Visit 19 (day 28) and Early Withdrawal Visit (EWV). Symptom directed physical examinations may be conducted as required during the study (visits 4 to 16). Requirements for the physical examination are specified in the SRM.
- E. Systolic blood pressure (SBP) and diastolic blood pressure (DBP) (mmHg), heart rate (beats per minute [bpm]), body temperature (°C), respiratory rate (breathes per minute) and weight (kg). To be performed within 4 hours prior to the first daily dosing on Visit 4 (day 1) through to Visit 17 (day 14) and within 4 hours before the time dosing would have occurred on Visit 18 (day 15). On days where the following assessments are done the order should be: vital signs before blood draws for PK or safety assessments.
- F. PKs will be performed as noted in the PK table. A single pre-dose PK sample will be collected on each of Days 12 & 13, and serial PK blood sampling will occur on Day 14 (see PK table below). At EWV a PK sample will be taken before the time of the planned daily dosing. If this is not possible, a spontaneous PK sample will be taken.

- G. Sputum smear microscopy and molecular rapid test for confirmation of Mycobacterium tuberculosis and rifampicin susceptibility (GeneXpert). If the first spot sputum or overnight sputum sample shows an unfavourable result, the tests may be repeated on a freshly collected spot sputum or overnight sputum sample and that result used instead.
- H. ). Refer to [Appendix 3](#) for details.
- I. Urine drug screen: cocaine, amphetamines and opiates. Urine drug screen can be repeated at Visit 2 (day -2) for participants who were not hospitalized at Visit 1 (day -9 to -3).
- J. CCI
- K. [REDACTED]

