## 5.6. Dose Justification

A population pharmacokinetic model was developed based on preliminary concentration-time data obtained in the FTIH study. The model was used to simulate loading and maintenance doses for GSK3036656 based on the EBA study design and accounting for

the effect of renal impairment on exposure (preliminary data suggest GSK303656 is > 70% renally excreted). A target exposure for efficacy of 1.74 ug.h/mL was set based on the exposure associated with efficacy in a mouse infection model and the target attainment rate was defined as the percentage of participants with an AUC0-24 greater than this target exposure. Exposure limits of AUC0-24 of 15 ug.h/mL and Cmax of 1.5 ug/mL were set, based on information in Section 3.3.

A loading dose of GSK3036656 may be administered on the first day (or over multiple days where required in order to not exceed AUC and Cmax exposure limits) of study treatment administration in each cohort. The long half-life of GSK3036656 (45 hours) means that subjects will take up to 10 days to reach steady-state concentrations, which is not optimal for a 14-day treatment study. A loading dose will allow participants to reach steady-state concentrations in 2 to 3 days for a given maintenance dose regimen.

The probability rates for individual participants to exceed GSK3036656 exposure limits and achieve the efficacy target for proposed loading and maintenance dose regimens are shown in Table 1.

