## 8.2. Individual/Cohort Stopping Criteria

For an individual study participant, stopping criteria include, but are not limited to:

- Severe signs or symptoms, or significant changes in any of the safety assessments that put the safety of the individual at risk (e.g. ECG, vital signs, laboratory tests etc.), as judged by the Investigator, in consultation with the Medical Monitor if necessary.
- Any unacceptable adverse event that is thought to be related to the investigational product and any general safety finding that, in the opinion of the Investigator, gives cause for concern may result in the withdrawal of subject(s) and/or the study being paused or terminated and/or a dose adjustment.

Dose escalation will be stopped if any of the following occurs in a cohort:

1. There is substantially increased incidence and/or severity of clinically significant adverse events or withdrawals possibly related to GSK3036656 in the GSK3036656 treatment subgroup at the last dose level administered as compared to the SoC subgroup. The Dose Escalation Committee in conjunction with the study Investigator will determine the significance of the adverse events or withdrawals and make a decision about whether stopping further dose escalation is necessary.
2. At least one subject has a plasma AUC0-24 or Cmax higher than the exposure limits set in Section 5.6.

If dose escalation is stopped due to reasons 1 or 2 above occurring at the last dose, dosing at a lower level could be allowed by the Dose Escalation Committee. The Dose

Escalation Committee will decide whether dosing at such level could be done and will select the dose to be administered.

Further details regarding dose escalation and the Dose Escalation Committee composition and remit are in Section 11.

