

and GSK Medical Governance approval is granted (see below)
 
 
• If restart/rechallenge not allowed per protocol or not granted, permanently discontinue study treatment and continue participant in the study for any protocol specified follow up assessments
 
 
MONITORING:
 
For bilirubin or INR criteria:
 
 
• Repeat liver chemistries (include ALT, AST, alkaline phosphatase, bilirubin) and perform liver event follow up assessments within 24 hrs
 
• Monitor participants twice weekly until liver chemistries resolve, stabilize or return to within baseline
 
• A specialist or hepatology consultation is recommended
 
 
For All other criteria:
 
 
• Repeat liver chemistries (include ALT, AST, alkaline phosphatase, bilirubin) and perform liver event follow up assessments within 24-72 hrs
 
• Monitor participants weekly until liver chemistries resolve, stabilize or return to within baseline
 
	
 
• Record alcohol use on the liver event alcohol intake case report form (CRF) page
 
 
For participants on GSK303656 arm
 
 
• Viral hepatitis serology
 
• Obtain blood sample for pharmacokinetic (PK) analysis as soon as possible, and certainly within 14 days after last dose
 
• Serum creatine phosphokinase (CPK) and lactate dehydrogenase (LDH).
 
• Fractionate bilirubin, if total bilirubin <math>\geq 2 \times \text{ULN}</math>
 
• Obtain complete blood count with differential to assess eosinophilia
 
 
For bilirubin or INR criteria:
 
For participants on GSK303656 arm only
 
 
• Auto-immune screen: Anti-nuclear antibody, anti-smooth muscle antibody, Type 1 anti-liver kidney microsomal antibodies, and quantitative total immunoglobulin G (IgG) or gamma globulins.
 
• Serum paracetamol/acetaminophen adduct high performance liquid chromatography (HPLC) assay (quantifies potential acetaminophen contribution to liver injury in participants with definite or likely acetaminophen use in the preceding week [James, 2009]).
 
• Liver imaging (ultrasound, magnetic resonance, or computerised tomography) and /or liver biopsy to evaluate liver
 

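### Exposure is measured only on Days 14-15, and a participant who stops GSK3036656 before Day 12 but is retained on standard of care may give no PK sample at all

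*Protocol*

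**What the plan says.** The sampling schedule is late and short. Under SoA footnote F, "A single pre-dose PK sample will be collected on each of Days 12 & 13", and "serial PK blood sampling will occur on Day 14", with the 24-hour sample falling on Day 15. Nothing is scheduled before Day 12.

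For participants who stop the drug early, the protocol gives separate rules:

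- **Leaves the study.** SoA footnote F: "At EWV a PK sample will be taken before the time of the planned daily dosing", or a spontaneous sample if that is not possible. A QTc stop under Section 8.1.2 means withdrawal from the study, so it falls here.
- **Liver stopping event on GSK3036656.** Appendix 7 requires a "blood sample for pharmacokinetic (PK) analysis as soon as possible, and certainly within 14 days after last dose", although the participant continues in the study.
- **Stops, stays and is placed on standard of care.** Section 8 says of stopping treatment that "this does not automatically result in the participant being withdrawn from the study" and asks investigators to try to keep the participant. It then says "GSK3036656 pharmacokinetic assessments are not required, since the participant is not being dosed with GSK3036656".
- **Haematology stop.** Section 8.1.3 says only that the investigational product is discontinued. Section 3.3.1 says such participants are withdrawn from the study.

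Section 8.2 stops escalation if "At least one subject has a plasma AUC 0-24 or C max higher than the exposure limits set in Section 5.6". Section 11 bases the next dose on population PK modelling where feasible, with a 10% ceiling on the predicted chance that an individual exceeds a limit. The dose escalation committee (DEC) needs PK from at least 7 participants on drug and selected safety data from everyone in the cohort.

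**The concern.** Section 8 excuses PK because dosing has ended. For a drug with a 45-hour half-life that is a weak reason: most of the drug is still in plasma the next day. The same event, an early permanent stop, leads to a sample or to none depending on whether the participant leaves the study and which organ system was involved. The outcome that Section 8 prefers, retention, is the one that can yield the least exposure data.

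At stake is the exposure review. If stopping is related to exposure, the participants missing from the PK data are not a random subset. The DEC would be judging exposure mainly in people who tolerated about two weeks of dosing, and no text in the protocol or SAP requires it to be shown who is missing. Under the SAP (Section 4), an early stopper with no evaluable sample is outside the PK population. The SAP table of exclusions from that population (Table 1.13) is marked for the final deliverable only.

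**Working it through.** The documents give no figure for this point, so there is none to reproduce. The check sets the rules side by side and adds simple arithmetic.

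**1. Who gives a sample after stopping before Day 12**

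| Route | In the study afterwards? | PK sample | Source |
|---|---|---|---|
| Leaves the study, including QTc stop | No | One, at early withdrawal visit | SoA footnote F; Section 8.1.2 |
| Liver stopping event | Yes | One, within 14 days of last dose | Appendix 7 |
| Haemoglobin or neutrophil criterion | Unclear: 8.1.3 and 3.3.1 differ | Unclear | Sections 8.1.3, 3.3.1 |
| Other stop, retained, placed on standard of care | Yes | None required | Section 8 |

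**2. What the exposure rule can use.** AUC0-24 and Cmax are derived by non-compartmental analysis (Protocol 10.3.1; SAP 12.6.5), and the only serial profile is on Days 14-15. A single early withdrawal sample yields neither quantity. A stop on Day 12 or 13 leaves troughs only. The measured-exposure rule therefore lacks a value for every participant who stops before the Day 14 profile, including those who withdraw and do give a sample.

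**3. Drug remaining after the last dose.** Input: half-life 45 h (Section 5.6). Assuming single-exponential decline, the fraction remaining is 0.5^(h/45):

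- 24 h: 0.5^(24/45) = 0.69
- 48 h: 0.5^(48/45) = 0.48
- 72 h: 0.5^(72/45) = 0.33
- 14 days (336 h): 0.5^(336/45) = 0.006

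A sample in the first days after stopping carries information on exposure. One at the outer edge of the liver window carries very little.

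**4. How many can be missing.** Inputs: 9 to 15 on drug per cohort (Section 5.1) and a minimum of 7 with PK (Section 11). The DEC minimum is met with 9 - 7 = 2 or 15 - 7 = 8 participants unsampled. If exactly one participant would have exceeded a limit, and missingness were unrelated to exposure, that one would be missed with probability 2/9 = 22% or 8/15 = 53%. These are the extremes that the minimum permits, not forecasts.

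**5. Worst case for the one-participant rule.** Assume 9 on drug, independent participants, individual exceedance probability p, and that the most exposed participant is always the one who stops early. The trigger probability falls from P(at least 1 of 9) = 1 - (1 - p)^9 to P(at least 2 of 9):

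| Assumed p | All 9 measured | Most exposed missing |
|---|---|---|
| 1% | 8.6% | 0.3% |
| 5% | 37.0% | 7.1% |
| 10% | 61.3% | 22.5% |

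Nothing in the documents shows that the most exposed participant stops early. Section 5.6, Table 1 gives exceedance rates below 1% for maintenance doses up to 20 mg, and 6.9% (Day 1) and 5.8% (Day 14) for the 30 mg regimen. By step 2, one added sample would not recover this loss.

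**The case against.** A reader might infer that dose escalation cannot see participants who stopped for toxicity. The documents do not support that. Section 11 requires safety data from all participants in the cohort. Section 8.2 has a separate rule for an excess of adverse events or withdrawals that does not depend on PK, and Section 8.3 stops the trial for certain related events. Only the exposure criterion lacks a value.

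A reader might also infer that the difference between staying and leaving causes the blind spot, or that one more sample would restore the rule's chance of triggering. Neither follows. Withdrawn participants are equally without an AUC0-24 or Cmax, and a single concentration supplies neither.

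The liver window should not be over-read as evidence that late samples measure exposure. Appendix 7 describes its follow-up assessments as meant to investigate aetiology.

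There is also discretion. PK that is not required is not forbidden. Section 9 lets assessment timing change without an amendment, Section 11 lets the DEC add PK for later cohorts, and Appendix 5 provides for extra measurements to clarify an adverse event. The DEC charter and the population PK analysis plan are separate documents and may already say how early stoppers are handled.

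These points narrow the gap without closing it. The discretionary routes do not guarantee a sample at the time of stopping, and the waiver in Section 8 tells sites the opposite.

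**Conclusion.** The point holds in a limited form. The Section 8.2 exposure rule has no measured value for anyone who stops before the Day 14 profile. Within that group, a participant who stops before Day 12 outside the liver pathway, is retained and moves to standard of care need give no PK sample. The stated reason fails on the protocol's own half-life, with about 69% of drug left at 24 hours and 33% at 72 hours. The DEC minimum lets up to 2 of 9 or 8 of 15 go unsampled. Whether haematology stoppers belong to this group cannot be settled from the text, because Sections 8.1.3 and 3.3.1 conflict.

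The likely size of any effect on dose selection is unknown: the documents do not say how often participants stop early or whether stopping tracks exposure. The trigger probabilities are a worst case that a single sample does not recover. The gain is confined to the population PK model, which is the main basis for escalation (Protocol Section 11; SAP 3.1). If the fallback dose-exposure regression is used instead, it needs AUC and Cmax values and one concentration does not enter it. This is a cheap improvement worth making, not a flaw that undermines the escalation scheme.

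**What to change.** Reconcile Section 8, SoA footnote F and Appendix 7 so that the single PK sample already specified for the early withdrawal visit (about 2 mL, with time of last dose recorded) is also taken when GSK3036656 is permanently stopped and the participant stays in the study. Remove the Section 8 waiver for that sample only. Where Appendix 7 already requires a sample, one tube can serve both purposes.

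Reconcile Sections 8.1.3 and 3.3.1 on whether a haematology stop means leaving the study. Which is intended is for the sponsor to decide.

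Include the sample in the population PK data that the DEC reviews. Align SAP 9.1.4, which limits PK data to those recorded up to the intercurrent event. State there that a post-stop sample feeds the population model but not the non-compartmental or trough analyses.

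Give the DEC a list of participants who stopped before the Day 14 profile, with model-estimated exposure and its uncertainty. An estimate from one sample is pulled towards the population average, so it should not be read as an observed AUC0-24 or Cmax.

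The cost is a small amendment, one short listing, and one extra tube per early stopper, which can be drawn with the safety bloods.
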